6.3.4 Visual Acuity

For this outcome it is important to know the percent of subjects with changes, improved or decreased, and the magnitude of the change. To summarize improvement, decrease, or no change at each follow-up visit each eye will be scored as a +1 for an increase in visual acuity, -1 for a decrease in visual acuity, and 0 for no change. Counts and percents will be used to summarize change in visual acuity for both the treatment and control eye. As with the NIH CC and DEWS, the control eye change will be subtracted from the the treatment eye change and a sign test will be conducted.

To estimate a the magnitude of change in acuity, Snellen Chart scores will be converted to LogMAR value. The change in acuity at follow-up for each eye will then be calculated as baseline LogMAR - follow-up LogMAR. The treatment eye change - the control eye change will then be used to conduct a Wilcoxon signed-test.

6.3.5 Effect of pAF on the Corneal Surface

Changes in the surface of the cornea will be measured using epithelial staining and graded on the following scale: Trace, 1+, 2+, 3+, 4+, Confluent. An improvement at follow-up will be considered to be movement to a lower grade. The treatment and control eyes will be scored at each visit with a +1 for improvement, -1 for decline, and 0 for no change. The number of treatment and control eyes improving and declining at each visit will summarized using 95% confidence intervals. To test for changes within patients the control eye will be subtracted from the treatment eye and a sign test will be conducted.

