5.4 Concomitant Medications and Procedures

Only medications with ocular effects will be recorded at screening and at subsequent study visits. These medications will be recorded in the medical record and appropriate CRF.

Patients may use non-medicated saline eye drops (artificial tears), provided they are applied in both eyes greater than 30 minutes following the application of the study eye drops.

All other eye drops, other than non-medicated saline eye drops, are prohibited while the patient is on study. If the patient is on medicated eye drops, a seven day washout is required before starting treatment. Patients can enroll if they have bilateral punctal plugs or if puncta were previously thermally cauterized, but the insertion of punctal plugs or cauterization is not allowed while the subject is on study.

5.5 Assessment of Response:

Assessment of response will be performed at 30 ± 3 , 60 ± 3 and 100 ± 3 days after initiation of therapy with pAF. The response is a combination of the NIH CC assessments and the ophthalmologic assessment (DEWS evaluation) as follows:

- NIH Consensus Conference (CC) for assessment of response in chronic GVHD
- Ophthalmologic assessment: Dry eye assessment will be performed over the course of four eye exams, including a baseline comprehensive eye exam (including a dilated fundus examination), and three follow-up exams (without dilation) on Day 30 ± 3 , Day 60 ± 3 and Day 100 ± 3 . Signs and symptoms of dry eye will be assessed at each exam using the grading scale provided by the International Dry Eye Workshop (DEWS) 2007 report.¹ DEWS assessment will include visual symptoms, severity and frequency of discomfort, conjunctival injection, conjunctival staining (using NaFl), corneal staining (using NaFl), corneal/tear signs (including filamentary keratitis and debris), the eyelids and meibomian glands, and fluorescein tear break-up time (TFBUT). Each sign/symptom will be graded on a scale of 1 to 4, with 4 being most severe. A total score will be taken at each exam, and a cumulative decrease in overall score >2 will constitute improvement with treatment. Note: Schirmer testing will not be performed or graded, as it has no proven value in ocular chronic GVHD.

Responders would be defined as a one point improvement in the dry eye grading scale (DEWS), without worsening in the eye score (NIH Consensus Criteria Ocular Assessment).

5.6 Assessment of Secondary Endpoints:

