6.3 Secondary Outcome(s) Analyses

6.3.1 NIH Consensus Criteria Ocular Score of Chronic GVHD

The NIH CC will be summarized as above. At each follow-up visit, 30 days, 60 days, and 100 days, the percent of treated eyes that have improved and progresses will be summarized using 95% confidence intervals. To test for a change within participants a sign test will be conducted. An improvement in an eye will be coded as a +1, symptom progression in an eye will be coded as -1, and no change coded as 0. A score will be created for each participant by subtracting the control eye from the treatment eye. Given the sample size it is likely we will use an exact binomial p-value.

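### SAP 6.3.5 codes each eye's staining change as +1/0/-1 before subtracting, so unequal changes in the same direction become ties and the corneal test loses power

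*SAP*

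**What the plan says.** SAP 6.3.5 has staining "graded on the following scale: Trace, 1+, 2+, 3+, 4+, Confluent". The size of a move does not matter: "An improvement at follow-up will be considered to be movement to a lower grade". Each eye is then reduced to a direction code: "The treatment and control eyes will be scored at each visit with a +1 for improvement, -1 for decline, and 0 for no change". The within-patient comparison is: "To test for changes within patients the control eye will be subtracted from the treatment eye and a sign test will be conducted".

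That last sentence does not say which quantity is subtracted. It follows directly on the coding, and the parallel rule in SAP 6.3.1, repeated in 6.3.2, codes each eye and then says: "A score will be created for each participant by subtracting the control eye from the treatment eye". The natural reading is that the codes are subtracted, not the grades.

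The only other summary in 6.3.5 is the number of eyes improving and declining, with 95% confidence intervals. For visual acuity, SAP 6.3.4 says "it is important to know the percent of subjects with changes, improved or decreased, and the magnitude of the change" and adds a second analysis on LogMAR: "The treatment eye change - the control eye change will then be used to conduct a Wilcoxon signed-test". SAP 6.3.6 also tests a between-eye difference in size, using pain slopes. The signed-rank test in protocol section 6 is named for the NIH eye and DEWS scores, not for staining.

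**The concern.** The objective is the effect of pAF on the corneal surface. With each participant as their own control, that effect is the between-eye difference in change. Coding before subtracting discards this difference whenever both eyes move the same way. A pAF eye that clears several grades beside a saline eye that clears one is recorded as no difference.

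Some improvement in saline eyes is plausible. They receive a drop twice daily, any one-grade fall counts, and protocol 5.4 adds: "Patients may use non-medicated saline eye drops (artificial tears), provided they are applied in both eyes". If it is common, a null corneal result could come from the scoring rule and be read as an absence of effect.

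**Working it through.** **Plan's own figure.** None is given for the corneal outcome. The sample-size statement (protocol section 6, SAP section 7) concerns McNemar's test on the primary endpoint. It serves here only to check the method, since exact McNemar and the exact sign test are the same calculation. With independent eyes and two-sided 0.05:

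- 60% vs 5%: discordant rates 0.60×0.95=0.57 and 0.05×0.40=0.02. Exact power at n=15 is 85.3%, and the smallest n reaching 80% is 14.
- 50% vs 5%: discordant rates 0.475 and 0.025. Exact power at n=19 is 83.1%, and the smallest n reaching 80% is 19.

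The stated 15 and 19 are therefore reproduced as giving at least 80%.

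**Step 1: the rule by arithmetic.** Number the grades Trace=0, 1+=1, up to Confluent=5. Change = baseline minus follow-up. The records below are constructed, because the documents hold no staining data.

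| pAF eye | Saline eye | SAP score | Difference in grade change |
|---|---|---|---|
| 4+ to Trace | 4+ to 3+ | (+1)-(+1)=0 | 4-1=+3 |
| 3+ to 1+ | 3+ to 2+ | (+1)-(+1)=0 | 2-1=+1 |
| 2+ to 3+ | 2+ to Confluent | (-1)-(-1)=0 | -1-(-3)=+2 |
| 3+ to 1+ | 3+ to 3+ | (+1)-0=+1 | 2-0=+2 |

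The first three leave the sign test; the fourth stays in. With both eyes starting at 4+, there are 6×6=36 follow-up pairs. Both eyes improve in 4×4=16 of them, by unequal amounts in 16-4=12, and all 12 score 0. As the limiting case, if all 15 participants followed the first row, the SAP test would have no informative pairs (p=1). The sign test on grade-change differences would give p=2×0.5^15=0.00006.

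**Step 2: a two-rate model.** Assume independent eyes, no declines, pAF eyes improving with probability 0.60, saline eyes with probability q, and a larger gain in the pAF eye whenever both improve. That last assumption favours the alternative score. The SAP coding has favourable pairs 0.60(1-q) and unfavourable pairs 0.40q. Using grade differences adds the 0.60q joint improvements to the favourable side. Exact two-sided power at n=15:

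| q | SAP coding | Grade difference |
|---|---|---|
| 5% | 85.3% | 88.9% |
| 10% | 71.6% | 80.9% |
| 20% | 44.0% | 65.5% |
| 30% | 22.7% | 51.7% |

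Both columns fall because the pAF rate is held fixed while q rises. The gap between them is the cost of the coding.

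**Step 3: simulation on the six grades.** Assumptions: latent baseline mean 3.2, between-participant SD 0.8, grading SD 0.5 per exam, SD of shared change 0.5, true pAF advantage 1 grade, exact two-sided 0.05, n=15. The mean shared change sets how many saline eyes improve.

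| Mean shared improvement (grades) | Saline eyes improving | SAP coding | Sign test on grade difference |
|---|---|---|---|
| -0.5 | 13% | 66% | 69% |
| 0 | 29% | 61% | 72% |
| 0.5 | 49% | 46% | 70% |
| 1 | 71% | 16% | 69% |

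In the last three rows, 13%, 27% and 45% of participants score 0 although their eyes' grade changes differ.

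With baseline mean 2.0, both tests lose power at the higher improvement rates because eyes reach the bottom of the scale: 39% vs 55% at 49% of saline eyes improving, and 11% vs 40% at 69%. With no pAF effect, type I error stays below 4% for both scores. None of these figures allows for the Bonferroni-Holm adjustment that SAP 5.3 applies to secondary endpoints.

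**The case against.** The other side has four points.

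- **The rule is not blind to every benefit.** A reader might infer that it registers only eyes moving in opposite directions. That is wrong: improved against unchanged, and unchanged against worsened, both count. If saline eyes mostly stay put, the test captures the effect. This stands.
- **Shared improvement is not shown to be expected.** Lubricant drops more than three times a day are one route to eligibility, and artificial tears may continue, so lubrication may already be in the baseline. The washout of medicated drops could push both eyes the other way. The only control-eye rate in the documents is 5%. It belongs to the primary composite, but if it held for staining the loss would be about 4 points. This stands as a limit on the size, not on the arithmetic of the rule.
- **It is an efficiency choice.** This is one of six secondary outcomes in a pilot, with no power claim attached. SAP 6.3.1 and 6.3.2 use the same coding, LogMAR is numeric, and staining grades have no stated equal spacing. This stands in part. However, a sign test on the grade difference needs equal steps only when the two eyes start at different grades.
- **Other outputs would reveal the problem.** Per-eye counts would show both eyes improving, and SAP 1.1 allows labelled exploratory analyses. The counts use the same codes, though, so they cannot show that one eye improved more. A later analysis would carry the label of unplanned.

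**Conclusion.** The concern holds as a loss of power on a secondary outcome. Unequal changes in the same direction are scored as ties, and nothing else planned in 6.3.5 recovers them. The test stays valid, and type I error is not inflated.

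The size is conditional on a rate the documents do not give. Under the simulation assumptions, the loss is about 3 to 4 points if 13% of saline eyes improve by a grade or more, 11 points at 29%, 24 at 49% and 53 at 71%. The grade-difference sign test had the higher power in every setting examined with a pAF effect, at baseline means of both 3.2 and 2.0.

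A reader might conclude that the planned test will lose most of its power. The documents do not support that: it requires improvement in a large majority of saline eyes, and the plan neither states nor implies such a rate. Changing the score is worthwhile because it is cheap, not because a large loss has been shown.

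**What to change.** In SAP 6.3.5, before unblinding:

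1. Number the grades in order, and state how a cornea with no staining is coded, since the printed scale starts at Trace.
2. Compute each eye's change as baseline grade minus follow-up grade.
3. Form treatment-eye change minus control-eye change, and apply the exact sign test to it. A signed-rank test is the alternative, as 6.3.4 intends for acuity. Name one.
4. Keep the +1/0/-1 codes for the descriptive counts of eyes improving and declining.

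The cost is a small change of wording and a few lines of code, with no new data, visits or participants. The downside is small: when the two eyes start at different grades, comparing their changes treats one grade step as equal along the scale. The signed-rank version relies on that more than the sign test does.

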6.3.6 Pain

Change in pain will be calculated from the patient diaries. A first level summary of pain will be to create median pain scores by eye for each week. Median trace plots and side-by-side box

plots will then be used to display the change in pain over time for treatment and control eyes.

The individual pain scores for each eye will be used to estimate a regression slope for each eye with pain as the outcome and day of treatment as the explanatory variable. The estimated slope of the control eye will be subtracted from the slope of the treatment eye and a Wilcoxon signed-rank test will be conducted.

6.4 Safety Analyses

The proportion of subjects who experience adverse events and serious adverse events will be summarized descriptively; no inferential tests will be performed.

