This includes the measurement of QOL with the FACT-G tool, patient reported pain assessment and measurement of visual acuity by ophthalmology.

5.7 Assessment of Safety:

Safety and tolerability will be evaluated by the investigator from the results of reported signs and symptoms, scheduled physical examinations, vital sign measurements, and clinical laboratory test results done as standard of care at day 30 ± 3 , day 60 ± 3 and day 100 ± 3 after initiation of pAF therapy. More frequent safety evaluations may be performed if clinically indicated or at the discretion of the investigator. SAEs will be reported within 24 hours of discovery to the central Data Coordinating Center.

Toxicity will be reported using Common Terminology Criteria for Adverse Events (CTCAE) version 4. Only ocular AEs will be collected.

An AE may consist of the following:

1. A new event which was not pre-existing at initial study drug administration.
2. A pre-existing event which recurs with increased intensity or increased frequency subsequent to study drug administration.

3. An event which is present at the time of study drug administration which is exacerbated following initial study drug administration.

A Serious Adverse Event (SAE) is defined by FDA and NCI as any adverse drug event (experience) occurring at any dose that in the opinion of either the investigator or sponsor results in any of the following outcomes:

1. Death
2. Life-threatening adverse drug experience
3. Inpatient hospitalization or prolongation of existing hospitalization (for > 24 hours)
4. Persistent or significant incapacity or substantial disruption of the ability to conduct normal life functions
5. Congenital anomaly/birth defect
6. Important Medical Event (IME) that may not result in death, be life threatening, or require hospitalization may be considered a serious adverse drug experience when, based upon medical judgment, it may jeopardize the patient or subject and may require medical or surgical intervention to prevent one of the outcomes listed in this definition

IRB Notification: Events meeting the University of Utah IRB reporting requirements (<http://www.research.utah.edu/irb/>) will be submitted through the IRB's electronic reporting system within 10 working days.

Reporting will be performed according to FDA guidance (<https://www.fda.gov/downloads/regulatoryinformation/guidances/ucm126572.pdf>)

5.8 Discontinuation of Study Drug:

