1.2 Auxiliary/Other Documents

The following documents were reviewed in preparation of this SAP:

- Protocol: A Randomized, Double-Blinded, Placebo-Controlled Study for the Treatment of Ocular Chronic Graft-Versus-Host Disease (GVHD) with processed Amniotic Fluid (pAF) Drops .
- Case Report Forms (CRFs) for the Ocular GVHD protocol

The reader of this SAP is encouraged to read the protocol for details on the conduct of this study, and the operational aspects of clinical assessments.

It is possible that, due to updates or identification of errors in specific statistical software discussed in this SAP, the exact technical specifications for carrying out a given analysis may be modified. This is considered acceptable as long as the original, prespecified statistical analytic approach is completely followed in the revised technical specifications.

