2 STUDY OBJECTIVES AND OUTCOMES

2.1 Study Objectives

2.1.1 Primary Objective(s)

The primary objectives of the Ocular GVHD trial are:

1. To determine the safety of pAF in patients with ocular chronic GVHD
2. To determine the clinical effects of pAF in ocular chronic graft versus host disease

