3 STUDY DESIGN AND METHODS

3.1 Overall Study Design

This is a randomized, double-blinded, placebo-controlled study of the efficacy of pAF in patients with hematologic malignancies who have undergone Allogeneic Hematopoietic Stem Cell Transplantation (HSCT) and are diagnosed with chronic GVHD of the eye. Patients will be allowed to continue the use of non-medicated lubricant eye drops (artificial tears) for ocular GVHD treatment prior to participating in this study. Patients are allowed to resume the use of eye drops after the 30 day treatment period at the discretion of the treating physician.

Participants will serve as their own control. A person will have one eye randomized to receive pAF and the other eye will receive saline drops.

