3.3 Treatment Masking (Blinding)

How are handling treatment assignment in the database? We are going to need to know more than left vs. right. Do we have the treatment labels entered as a form? Why do I have so many questions?

The ocular GVHD study will be performed in a double-blind fashion. All study personnel, including investigators and research coordinators will be blinded as to which eye is receiving the active treatment and which is receiving control.

Of necessity, biostatisticians involved in presenting interim analyses to the DSMB will be aware which subjects have received “Treatment A” and which have received “Treatment B”, but they will not be aware of the identity of the two arms.

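### The stated AE and SAE summary counts subjects, not eyes, so it does not clearly compare pAF with saline; SAP 5.3 also conflicts with 6.4 on safety p-values

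*SAP*

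**What the plan says.** The first-listed primary objective in SAP 2.1.1 is: "To determine the safety of pAF in patients with ocular chronic GVHD". The design is paired by eye (SAP 3.1): "A person will have one eye randomized to receive pAF and the other eye will receive saline drops". Protocol 5.7 limits event collection: "Only ocular AEs will be collected".

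The only statistic given for events is the one in SAP 6.4: "The proportion of subjects who experience adverse events and serious adverse events will be summarized descriptively; no inferential tests will be performed". The same sentence stands in Protocol 6 and in the statistical row of the Protocol synopsis.

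Two other SAP sections bear on it:

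- SAP 4.2.4 assigns adverse-event analysis to the safety population and says results follow the treatment actually received. It defines that population as subjects who receive any study drug.
- SAP 5.3 says each safety comparison will carry an unadjusted p-value, with a Bonferroni-Holm adjustment if the DSMB or other reviewers ask for one.

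**The concern.** A participant who uses the drops as assigned has received both products, so grouping subjects by treatment received does not separate pAF from saline. The separation exists only at the level of the eye. The efficacy sections say so explicitly: SAP 6.2.1 and 6.3.5, for example, report treatment eyes against control eyes. SAP 6.4 does not.

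Read as written, the adverse-event figure leaves the within-person control unused and cannot show which product an excess of ocular events belongs to. In addition, SAP 5.3 and 6.4 give different instructions on whether safety p-values appear in the report.

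**Working it through.** **Starting point.** The plan contains no adverse-event rate or count, so there is no figure of its own to reproduce. The sample sizes are documented: 15 to 20 patients in the Protocol synopsis. All event counts and rates below are assumed, for illustration only.

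**Step 1: what the stated statistic can distinguish.** Among n participants, let b have an event in the pAF eye only, c in the saline eye only, and d in both.

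- Subject-level proportion (SAP 6.4 as written) = (b + c + d)/n
- pAF-eye proportion = (b + d)/n
- Saline-eye proportion = (c + d)/n
- Difference between eyes = (b − c)/n

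The first expression does not change when b and c are swapped, whatever their values. With 6 participants affected, one eye each (d = 0):

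| b, c | n = 15: subjects | n = 15: pAF v saline eye | n = 20: subjects | n = 20: pAF v saline eye |
|---|---|---|---|---|
| 6, 0 | 6/15 = 40% | 40% v 0% | 6/20 = 30% | 30% v 0% |
| 3, 3 | 6/15 = 40% | 20% v 20% | 6/20 = 30% | 15% v 15% |
| 0, 6 | 6/15 = 40% | 0% v 40% | 6/20 = 30% | 0% v 30% |

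At n = 15, one reported figure fits between-eye differences from +40 to −40 percentage points.

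**Step 2: the same in rates.** Assume event rates of 30% in pAF eyes and 5% in saline eyes.

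- Independent eyes: 1 − (0.70 × 0.95) = 0.335.
- Complete overlap (every saline-eye event in a participant who also has a pAF-eye event): 0.30.
- No overlap: 0.30 + 0.05 = 0.35.
- Expected number affected: 4.5 to 5.25 of 15, or 6 to 7 of 20.

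Reversing the two rates gives identical figures. Equal rates of 1 − √(1 − 0.335) = 0.1845 in each eye, independent, also give 0.335.

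**Step 3: does SAP 4.2.4 supply the eye-level rule?** It states an intent to separate by treatment. It can be met by counting each subject under both products, with events attributed to the eye concerned, but the text does not say this. The neighbouring definitions (SAP 4.2.2 and 4.2.3) speak of a subject's assigned arm, and no subject here has a single arm.

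**Step 4: the two rules on p-values.** SAP 6.4, Protocol 6 and the synopsis all say no inferential tests for AEs and SAEs. SAP 5.3 says unadjusted p-values for safety outcomes. Protocol 5.7 does take a wider view of safety ("Safety and tolerability will be evaluated by the investigator from the results of reported signs and symptoms", together with examinations, vital signs and laboratory results). But SAP 6.4 is the only safety analysis section, and it names no outcome other than AEs and SAEs.

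The difference would be visible in a report. If SAP 5.3 were applied with the exact McNemar test (an assumption, since it names no test), a 6 v 0 split would carry a two-sided p of 2 × (1/2)^6 = 0.031 and a 3 v 3 split p = 1.00. Under SAP 6.4 neither value would be reported.

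**The case against.** The strongest reply is that SAP 4.2.4 supplies the grouping and 6.4 only the statistic. Since everyone is assigned both products, grouping by treatment received makes sense only if events are attributed by eye. That is a fair reading of the intent. It stands to this extent: the gap is one of wording, and a sensible analyst might well report by eye anyway. It does not close the gap, because neither section states the rule.

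A reader might infer that the trial yields no product-specific information on harm. The documents do not support that. NIH eye score, DEWS, visual acuity, corneal staining and pain are all compared between eyes (SAP 6.2.1 and 6.3), and Protocol 5.9 counts worsening in the pAF-treated eye, using one unblinded person. None of these is a summary of adverse events, but they limit what is lost.

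A reader might also infer that the eye of onset is not recorded. That cannot be concluded. SAP 1.2 lists "Case Report Forms (CRFs) for the Ocular GVHD protocol", and those forms are not among the documents reviewed. The link from eye to product exists in the coded right and left boxes (Protocol 5.3, SAP 3.2.1). SAP 3.3 still carries an open note, "We are going to need to know more than left vs. right", but it concerns every analysis and is not evidence about adverse events in particular.

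On p-values, SAP 4.2.4 names adverse events and safety outcomes separately, so 5.3 could be meant for something else. Without any other safety outcome defined in the SAP, that reading has nothing to apply to. It is fair to add that three statements agree on no tests for AEs and SAEs, so 5.3 is the outlier and the direction of the correction is clear.

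**Conclusion.** The point holds as a gap in the written safety analysis, and it should be fixed before the analysis is run. As stated, the AE and SAE statistic pools pAF and saline. The one sentence that points towards separating them gives no eye-level rule. The conclusion rests on the paired-eye design and the wording of SAP 4.2.4 and 6.4. It does not depend on any assumed event rate, because the subject-level proportion is symmetric in the two eyes at every rate.

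The conflict between SAP 5.3 and 6.4 is a separate, smaller matter of consistency.

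The finding does not imply that safety needs formal testing, nor that confidence intervals should be excluded from a descriptive safety summary. The SAP already uses intervals as summaries in 6.3.1, 6.3.2 and 6.3.5. Confidence is moderate, mainly because the case report forms could not be seen.

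**What to change.** 1. In SAP 6.4, Protocol 6 and the Protocol synopsis, report descriptively the number and percentage of participants with at least one ocular AE, and with at least one SAE, in the pAF eye and in the saline eye.
2. Add a paired breakdown: pAF eye only, saline eye only, both, neither.
3. Keep a per-participant row for events that cannot be assigned to one eye. Some SAE criteria in Protocol 5.7 are of this kind, for example "Inpatient hospitalization or prolongation of existing hospitalization".
4. State in SAP 4.2.4 that treatment received applies per eye.
5. Confirm that the AE form records the eye, and add the field if it does not.
6. Amend the safety paragraph of SAP 5.3 to agree with 6.4 and the protocol: descriptive reporting, with no p-values for AEs and SAEs.

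The cost is one extra table, short wording edits in the two documents and possibly one form field. Sample size, visits and the efficacy analyses are unchanged.
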